7.5 Responder Analysis Set

Includes all subjects who had CMR or PMR **per central review** during the first **12** weeks after initiation of blinatumomab.

7.6 Safety Analysis Set

Includes all subjects who received blinatumomab. It is the same as FAS.

7.7 Pharmacokinetic Analysis Set

All subjects who received any infusion of blinatumomab and had at least one PK sample collected will be included in the Pharmacokinetic Analysis Set. These subjects will be evaluated for pharmacokinetics unless significant protocol deviations affect the data analysis or if key dosing, dosing interruption, or sampling information is missing.

7.8 Pharmacodynamic Analyses Set

All subjects who receive any infusion of blinatumomab and had at least one pharmacodynamic sample collected will be included in the Pharmacodynamic Analysis Set.

7.9 Interim Analysis Set

Not applicable

7.10 Subgroup Analyses

Subgroup analyses for primary and key secondary endpoints will be performed on the following categories:

- Age: < = 64 vs. 65-74 vs. \geq 75 years old
- Sex: male vs. female
- Race: white vs. others
- Geographic region: North America vs. Europe vs. Rest of the world
- Response to S1: PMR vs. NMR/PMD
- High-dose Cytarabine in S1: yes vs. no
- **Lymphoma type: Gray Zone Lymphoma Vs All other histologies of aggressive B-cell lymphoma**
(Note: primary Mediastinal B-Cell Lymphoma (PMBCL) and B-cell lymphoma, unclassifiable, with features intermediate between DLBCL and classical Hodgkin lymphoma are known as Gray Zone Lymphoma)
- Primary disease status: Relapsed vs. refractory (No Remission)

8. Interim Analysis and Early Stopping Guidelines

Not Applicable

9. Data Screening and Acceptance

9.1 General Principles

The objective of the data screening is to assess the quantity, quality, and statistical characteristics of the data relative to the requirements of the planned analyses. The database will be subject to edit checks outlined in the data management plan by Amgen Clinical Data Management (CDM) department. Any outstanding data issues will be communicated to CDM for resolution before the database is locked.

9.2 Data Handling and Electronic Transfer of Data

The Amgen Global Study Operations-Data Management (GSO-DM) department will provide all data to be used in the planned analyses. This study will use the RAVE database.

An Analysis Dataset for PK Concentrations (ADPC) will be provided to the appropriate Clinical Pharmacology Modeling and Simulation (CPMS) representative from Global Biostatistical Sciences.

9.3 Handling of Missing and Incomplete Data

Subjects **with no** post baseline disease assessments will be considered not to have achieved CMR.

The handling of incomplete and partial dates for adverse events and concomitant medications are described in [Appendix A](#). Handling of missing or incomplete data for exposure-response (E-R) analysis will be described in the E-R supplemental SAP (SSAP) or associated documents to support population PK/PD dataset generation and E-R analysis.

9.4 Detection of Bias

If applicable, the methods to detect bias are described in the analyses of particular endpoints.

9.5 Outliers

Any suspected outliers will be investigated by the study team and will be included in the database unless determined to be an error or there is supporting evidence or explanation to justify the exclusion. Any outliers excluded from the analysis will be discussed in the Clinical Study Report (CSR), including the reasons for exclusion and the impact of their exclusion on the study.

PK serum concentration data will be evaluated for outliers by visual inspection, and decisions to re-assay individual samples will be made in accordance with standard pharmacokinetic evaluation practice.

9.6 Distributional Characteristics

The statistical assumptions for analysis methods will be assessed. If the assumptions for the distributional characteristics are not met, these will be described, and further analyses may be carried out using data transformations or alternative analysis methods. The use of transformations or alternative analysis methods will be justified in the final study report.

9.7 Validation of Statistical Analyses

Programs will be developed and maintained, and output will be verified in accordance with current risk-based quality control procedures.

Tables, figures, and listings will be produced with validated standard macro programs where standard macros can produce the specified outputs.

The production environment for statistical analyses consists of Amgen-supported versions of statistical analysis software; for example, the SAS System version 9.4 or later.

10. Statistical Methods of Analysis

10.1 General Principles

This section specifies to the final analysis. Continuous variables will be summarized by the non-missing sample size (n), mean, standard deviation, median, first and third quartiles, minimum, and maximum. Categorical variables will be summarized by the n and percentage in each category. Time to event endpoints will be summarized with hazard ratios, Kaplan-Meier (KM) curves, KM proportions at select time points, KM quartiles (when estimable), the number of subjects with events, the number of subjects censored, and the pattern of censoring. Point estimates for efficacy endpoints will be accompanied by 2-sided 95% confidence intervals including estimates of KM quartiles ([Brookmeyer and Crowley, 1982](#)), KM proportions ([Kalbfleisch and Prentice, 1980](#)), and binomial proportions ([Clopper CJ and Pearson, 1934](#)).

10.2 Subject Accountability

The number and percent of subjects who were screened, **enrolled**, received protocol-specified therapy along with the reasons for discontinuing protocol-specified therapy and discontinuing study will be summarized. The number and percent of

subjects **enrolled** will be tabulated by study site. Key study dates for the first subject **enrolled**, last subject **enrolled**, and data cut-off date for analysis will be presented.

10.3 Important Protocol Deviations

Important Protocol Deviations (IPDs) categories are defined by the study team before the first subject's visit and updated during the IPD reviews throughout the study prior to database lock. These definitions of IPD categories, sub-category codes, and descriptions will be used during the course of the study. Eligibility deviations are defined in the protocol.

10.4 Demographic and Baseline Characteristics

Demographic (ie, age, age group, sex, race, ethnicity) and baseline disease characteristics will be summarized using descriptive statistics. If multiple races have been reported for a subject, the subject will be categorized as multiple races as well as by combination of races.

The baseline characteristics to be summarized include:

- Age
 - age group: < 65 vs. \geq 65-< 75 vs. \geq 75
 - summary statistics
- Sex: Male, Female
- Race
 - American Indian or Alaska Native
 - Asian
 - Black (or African American)
 - White
 - Other
- Geographic region
 - North America
 - Asia
 - Europe
 - Rest of the world
- Response to S1: PMR, NMR/PMD
- High-dose Cytarabine in S1: Yes, No
- Lymphoma type: Gray Zone Lymphoma Vs All other histologies of aggressive B-cell lymphoma.

(Note: primary Mediastinal B-Cell Lymphoma (PMBCL) and B-cell lymphoma, unclassifiable, with features intermediate between DLBCL and classical Hodgkin lymphoma are known as Gray Zone Lymphoma)

- Ann Arbor stage at diagnosis: I, IE, II, IIE, II bulky, III, IV
- Ann Arbor stage at relapse: I, IE, II, IIE, II bulky, III, IV
- IPI, R-IPI, aalIPI, NCCN-IPI at diagnosis
 - IPI- Low (0-1), Low-Intermediate (2), High-Intermediate (3), High (4-5)
 - R-IPI- Very good (0), Good (1-2), Poor (3-5)
 - aalIPI-(only for subjects <60 years: Low (0), Low-Intermediate (1), High-Intermediate (2), High (3)
 - NCCN-IPI-Low (0-1), Low-Intermediate (2-3), High-Intermediate (4-5), High > 6
- IPI, R-IPI, aalIPI, NCCN-IPI at relapse
- Primary disease status:
 - Relapsed
 - Refractory (no remission)
- Prior indolent lymphoma
 - Yes (follicular NHL, marginal zone, other)
 - No
- Extranodal disease: Bone Marrow, CNS, Liver/GI, Lung, Other
- Cell of Origin Determination: GCB, Non-GCB, ABC, Not done
- Bcl-2 rearrangement status: Positive, Negative, Indeterminate, Not Done
- Bcl-2 overexpression status: Positive, Negative, Indeterminate, Not Done
- Bcl-6 rearrangement: Positive, Negative, Indeterminate, Not Done
- Bcl-6 overexpression: Positive, Negative, Indeterminate, Not Done
- C-myc rearrangement status: Positive, Negative, Indeterminate, Not Done
- C-myc overexpression status: Positive, Negative, Indeterminate, Not Done
- Treated in S1 with: R-DHAP, R-ICE, R-GDP, R-ESHAP, Other
- Double hit: Yes, No, (Yes is defined by both C-myc and Bcl-6 overexpression and rearrangement are Yes; otherwise No)
- Triple hit: Yes, No, (defined as 'Yes' if all of Bcl-2, Bcl-6 and C-myc rearrangement are 'Yes', else 'No'.)
- NHL Subtype: 1) Diffuse large B-cell Lymphoma (DLBCL), NOS
 - 2) High grade B-cell Lymphoma with MYC and BCL2 and/or BCL6 Rearrangements
 - 3) Primary Mediastinal (Thymic) large B-cell Lymphoma
 - 4) T-cell Histiocytic large B-cell Lymphoma

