3.2 Sample Size

The sample size for the study is determined by a one-sample test of the rate of CMR during first 12 weeks after initiation of blinatumomab. With the one-sided type I error rate (α) set at 0.025, a null hypothesis response probability (π_0) of 15%, and an alternative response probability (π_1) of 40%, a sample size of 36 subjects will provide 90% power to reject the null hypothesis that the response probability is no more than 15%.

4. Study Endpoints and Covariates

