4.1.4 Exploratory Endpoints

- Pharmacodynamics, including descriptive analysis of quantitative and qualitative features of lymphocyte populations and serum or plasma concentrations of cytokines
- Response rates and duration according to COO designation and c-myc and bcl-2 rearrangement and over expression, R-IPI, Secondary IPI, NCCN IPI, as determined from pretreatment specimens

- Quantitative analysis of CT-DNA as determined by **analysis of tumor-associated mutations in CF CT-DNA** from plasma collected at various timepoints before, during, and after treatment

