4.2 Exploratory

- To characterize the pharmacodynamic effects of blinatumomab administered in temporal proximity to various S1 regimens
- To evaluate the response rate according to disease-specific features, such as cell-of-origin (COO), c-myc and bcl-2 rearrangements **and over expression, Revised International Prognostic Index (R-IPI), Secondary International Prognostic Index (IPI), National Comprehensive Cancer Network International Prognostic Index (NCCN IPI), first response status before blinatumomab, duration of first remission before blinatumomab**
- To evaluate the frequency of **tumor-associated mutations in cell-free (CF) circulating tumor (CT- DNA)** among subjects at various time points during and after salvage treatment
- To determine the incidence of anti-blinatumomab antibody formation

5. Hypotheses and/or Estimations

The complete metabolic response (CMR) rate during the first 12 weeks since starting blinatumomab will be estimated for blinatumomab monotherapy administered in the second salvage (S2) treatment of transplant-eligible subjects with relapsed or refractory (R/R) aggressive B-NHL who have not achieved CMR.

6. Definitions

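### SAP 10.4, baseline table only: the two-level double-hit and triple-hit flags report undetermined subjects as No, and the two definitions do not line up with each other or with the subtype row

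*SAP*

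**What the plan says.** All of this stands in the list of baseline characteristics in SAP Section 10.4.

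- **Double hit:** "Double hit: Yes, No, (Yes is defined by both C-myc and Bcl-6 overexpression and rearrangement are Yes; otherwise No".
- **Triple hit**, the next item: Yes "if all of Bcl-2, Bcl-6 and C-myc rearrangement are" Yes, and No in every other case. Overexpression is not mentioned.
- **Component markers:** Bcl-2, Bcl-6 and C-myc each have a rearrangement row and an overexpression row with four levels, for example "Bcl-6 rearrangement: Positive, Negative, Indeterminate, Not Done". None of these rows has a level called Yes.
- **NHL subtype:** one category is "High grade B-cell Lymphoma with MYC and BCL2 and/or BCL6 Rearrangements".

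Elsewhere, the exploratory objective (SAP 4.2) names features "such as cell-of-origin (COO), c-myc and bcl-2 rearrangements", and the exploratory endpoint (SAP 4.1.4) is "Response rates and duration according to COO designation and c-myc and bcl-2 rearrangement and over expression". Neither mentions double hit or triple hit. The protocol's own marker lists (Section 7.3.3 on medical history, and Table 10 on central laboratory samples) name bcl-2 and c-myc but not Bcl-6.

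**The concern.** A derived flag with only two levels must put every subject somewhere, and both rules put every subject who is not Yes into No. A subject with none of the markers tested is then counted together with a subject shown to be negative. The table would give no count of subjects whose status is unknown. The marker rows do not supply it, because they are one-marker totals and each flag depends on several markers jointly.

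Two further points concern the definitions. The double-hit wording, taken as written, sets an overexpression condition that the triple-hit line does not. It also leaves out Bcl-2, although the subtype row of the same table and the exploratory analyses use it. Two programmers could derive double hit differently, and a reader could not tell from the table which definition was used.

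At stake is how two descriptive rows are reported. No inference depends on them.

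**Working it through.** The documents state no figure for either flag, so there is none to reproduce. The check is a logic check of the rules, reading their Yes as Positive. The counts below are counts of possible marker patterns, not expected patient proportions.

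**1. Undetermined subjects reported as No.** Each marker has 4 levels, 3 of which are not Negative. A flag is undetermined when no required marker is Negative and not all are Positive.

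- Double hit, literal reading, 4 required markers: 4^4 = 256 patterns, 1 is Yes and 255 are No. Undetermined: 3^4 − 1 = 80 of the 255.
- Triple hit, 3 required markers: 4^3 = 64 patterns, 1 is Yes and 63 are No. Undetermined: 3^3 − 1 = 26 of the 63.
- The other No patterns (255 − 80 = 175 and 63 − 26 = 37) contain at least one Negative, and there No is correct.
- With every marker Not Done, both flags return No.

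**2. The two rules side by side.** Fully tested subjects with C-myc rearranged and Bcl-2 and/or Bcl-6 rearranged:

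| C-myc / Bcl-2 / Bcl-6 rearrangement | Double hit, literal | Double hit, rearrangement only | Triple hit |
|---|---|---|---|
| + / + / + | Yes only if C-myc and Bcl-6 overexpression are both Positive | Yes | Yes |
| + / + / − | No | No | No |
| + / − / + | Yes only if C-myc and Bcl-6 overexpression are both Positive | Yes | No |

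Over all six markers there are 4^6 = 4096 patterns, and triple hit is Yes in 4^3 = 64 of them (the three overexpression results are free). On the literal reading double hit is No in 60 of these 64: 4 × 4 − 1 = 15 combinations of C-myc and Bcl-6 overexpression that are not both Positive, times 4 levels of Bcl-2 overexpression. On the rearrangement-only reading the combination triple hit Yes with double hit No cannot occur.

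The second row of the table is No on double hit under both readings, although its marker pattern meets the wording of the subtype category.

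**3. Size.** SAP 3.2 states that "a sample size of 36 subjects will provide 90% power", so one subject coded differently moves a row by 1/36 = 2.8 percentage points. The documents give no marker frequencies or testing rates. As an illustration only, assume u of the 36 are undetermined on a flag and 4 are Yes (reported as 4/36 = 11.1%):

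| Assumed u | 36/(36 − u) | 4/(36 − u) |
|---|---|---|
| 6 | 1.2 | 13.3% |
| 12 | 1.5 | 16.7% |
| 18 | 2.0 | 22.2% |

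The last column is the percentage among determined subjects. The SAP does not promise that denominator, and u would differ between the two flags.

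**The case against.** The strongest case on the other side is that each rule is explicit, can be programmed as written, and feeds only a descriptive table. Several of its points stand.

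- **The markers are not misreported.** A reader might infer that untested markers are shown as No. They are not: each marker keeps Indeterminate and Not Done in its own row. Only the subject-level flag becomes No.
- **Not every incompletely tested subject is miscoded.** If C-myc is Negative and Bcl-6 is Not Done, No is correct.
- **The definitions do not strictly contradict each other.** A reader might infer that triple hit Yes with double hit No is a contradiction. The SAP nowhere says that triple hit is a subset of double hit, and the mismatch disappears if only rearrangement was meant.
- **Leaving out Bcl-2 is not shown to be an error.** A reader might infer that double hit must equal the subtype category. The SAP does not equate them, and the subtype row can still show a C-myc and Bcl-2 pattern. The exploratory objective and endpoint list c-myc and bcl-2 as features; they do not define double hit.
- **Yes against Positive is loose wording** that is unlikely to mislead a programmer.

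Two defences do not remove the point. The marker rows give separate totals, from which the number of undetermined flags cannot in general be recovered. The separate biomarker plan announced in SAP 10.5.5 may add detail on markers, but the rule for this table is set in Section 10.4.

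**Conclusion.** The point holds, as a minor one. The firm part is the default to No: under either reading of double hit, and for triple hit, a subject whose results rule out neither Yes nor No is reported as No. The mismatch between the two flags depends on taking the double-hit wording literally. The omission of Bcl-2 is a matter to reconcile, because it rests on the sponsor's intent.

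The number of subjects affected cannot be stated and could be zero. Undetermined subjects are plausible, because the protocol's marker lists do not name Bcl-6; the list in Section 7.3.3 gives examples, however, so it does not show that Bcl-6 went untested. Each recoded subject is worth 2.8 percentage points if 36 are analysed.

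A reader might infer some effect on the efficacy results. The documents do not support that: neither flag is a subgroup factor (SAP 7.10), enters the primary CMR analysis (SAP 10.5.1) or the sample size (SAP 3.2), or is named in the exploratory endpoints, which use the markers directly.

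**What to change.** Change the two definitions in SAP 10.4:

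- Add an Unknown level, with its count, to both flags. Yes if all required markers are Positive; No only if the available results rule out Yes; otherwise Unknown.
- State both flags on the same basis, rearrangement, and use the level name Positive in the rules. Overexpression stays in its own rows.
- Triple hit is then Yes if all three rearrangements are Positive, No if any is Negative, otherwise Unknown.
- Reconcile double hit with the subtype row, with the sponsor confirming whether Bcl-2 is to be included. If it is not: Yes if C-myc and Bcl-6 are both Positive, No if either is Negative, otherwise Unknown. If it is: Yes if C-myc is Positive and at least one of Bcl-2 and Bcl-6 is Positive; No if C-myc is Negative or both Bcl-2 and Bcl-6 are Negative; otherwise Unknown.

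The cost is two lines of SAP text, two derivations from fields that the table already lists, and the sponsor's confirmation. No new data are needed. The downside is that some subjects move from No to Unknown, possibly many if Bcl-6 was rarely tested.

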10.5 Efficacy Analyses

Efficacy analyses will be performed on the FAS unless specified otherwise.

10.5.1 Analyses of Primary Efficacy Endpoint

The percentage of subjects with a CMR by central review during the 12 weeks after initiation of blinatumomab will be summarized with an exact binomial 95% confidence interval using FAS. A summary of CMR during the treatment will also be provided using TDAS.

10.5.2 Analyses of Secondary Efficacy Endpoint(s)

Other secondary efficacy endpoints include ORR during the first 12 weeks of starting blinatumomab and during the treatment, PFS, duration of CMR, duration of response, successful mobilization rate, alloHSCT rate, autoHSCT rate and 100-day NRM after HSCT.

ORR during the first 12 weeks after initiation of blinatumomab and during the treatment will be summarized with an exact binomial 95% confidence interval.

PFS and OS will be summarized with the KM summaries.

Duration of CMR and duration of response will be summarized with the KM summaries using Responder Analysis Set.

AutoHSCT rate, alloHSCT rate and HSCT rate will be summarized with an exact binomial 95% confidence interval. AutoHSCT rate is the proportion of all subjects who achieve a response per investigator's review and undergo autoHSCT while in remission and without any other anti-cancer treatment, eg, all subject in the autoHSCT Analysis Set. Similarly alloHSCT rate will be analyzed with subjects in the alloHSCT Analysis Set. HSCT rate will be analyzed with subjects who are in either autoHSCT or alloHSCT Analysis Set. The rates are based on Responder Analysis Set. As a sensitivity analysis, HSCT (autoHSCT or alloHSCT) rate will be provided with the proportion of all subjects who had HSCT based on FAS.

Successful mobilization rate will be summarized based with an exact binomial 95% confidence interval. Successful mobilization rate is the proportion of subjects who initiated mobilization while in remission and without any other anti-tumor therapy, and the mobilization procedure has an outcome as 'Successful' as recorded on the mobilization CRF page based on Responder Analysis Set. As a sensitivity analysis, the proportion of subjects who initiated mobilization and the mobilization procedure

has **an** outcome as 'Successful' **as** recorded on **the** mobilization CRF page based on FAS will be provided.

The 100-day NRM after HSCT rate **based on subjects either in autoHSCT analysis set or alloHSCT analysis set** will be summarized with the cumulative incidence function with relapse or deaths due to relapse treated as competing risks. For this endpoint, time to non-relapse deaths will be measured starting from the date of HSCT.

10.5.3 Analyses of Patient Reported Outcomes and Other Health Related Quality of Life Endpoints

Not Applicable.

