4.1.2 Other Secondary Endpoints

- Objective response (OR; including CMR and PMR)
- PFS
- Overall survival**
- Duration of CMR for subjects who achieved CMR **per investigator's review** during the first **12 weeks** since starting blinatumomab
- Duration of response (DOR) for subjects who achieved response **per investigator's review during the first 12 weeks since starting blinatumomab**
- Successful mobilization rate (**defined as CD34+ cell 2x10⁶/kg**)
- Autologous HSCT (autoHSCT) rate among subjects with post –blinatumomab CMR+PMR **per investigator's review**
- Allogeneic HSCT (alloHSCT) rate among subjects with post-blinatumomab CMR+PMR **per investigator's review**
- 100-day non-relapse mortality (NRM) after HSCT
- Blinatumomab concentration steady state, clearance, and half life

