6.2 Efficacy Endpoints

Response rate will be based on the central review of radiographic assessment of PET-CT scans using the Lugano Classification. DOR, DOCR, PFS and HSCT related endpoints will be based on investigator's review of radiographic assessment of PET-CT scans using the Lugano Classification and clinical assessment.

100 Day non-relapse mortality (NRM) Rate after HSCT

Non-relapse mortality rate at 100 days after HSCT will be estimated using the cumulative incidence function with relapse or deaths due to relapse treated as competing risks. Only subjects who achieve a response **per investigator's review** and undergo autoHSCT are included. Only deaths without relapse are considered as events.

Allogeneic HSCT (alloHSCT) Rate

Allogeneic HSCT rate is the proportion of responder **per investigator's review** (subjects who achieved either CMR or PMR during the treatment) who have undergone alloHSCT **while in remission and without any other anti-cancer treatment**.

Autologous HSCT (autoHSCT) Rate

Autologous HSCT rate is the proportion of responder **per investigator's review** (subjects who achieved either CMR or PMR during the treatment) who have undergone autoHSCT **while in remission and without any other anti-cancer treatment**

Complete Metabolic Response (CMR)

CMR is determined by the central review of radiographic assessment of PET-CT scans using the Lugano Classification. Subject's CMR status is determined by whether the subject achieves CMR during the first 12 weeks of treatment since starting blinatumomab.

Complete Metabolic Response Rate (CMR Rate)

Complete metabolic response rate (CRR) is the proportion of subjects who have achieved CMR by the central review of radiographic assessment of PET-CT using Lugano Classification among all subjects in the respective analysis set.

Duration of Response (DOR)

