Duration of Response is calculated only for subjects who achieve a response (CMR or PMR) per **investigator's** review during the first **12 weeks** starting blinatumomab. The duration will be calculated from the date a response, CMR or PMR, is first achieved until the earliest date of a disease assessment indicating disease progression or death, whichever occurs first. **For diagnosis of progression of lymphoma, the progression per investigator's review of radiographic assessment of PET-CT using Lugano Classification will be used. In the absence of radiographic assessment during the long term follow up period, the clinical progression on the CRF page will be used.** Subjects who do not have a relapse event will be censored on their last **radiological non-missing evaluable tumor assessment date or last non-missing clinical assessment**. If the last disease assessment date is after the date that triggers the analysis, the subject will be censored **at the last radiological non-missing evaluable tumor assessment date or last non-missing clinical assessment** prior to the analysis trigger date. A sensitivity analysis will censor subjects who receive a HSCT at the time of HSCT unless there is no assessment after the HSCT, in which case the last **clinical or radiological non-missing evaluable tumor assessment** prior to the HSCT will be used as the censoring time.

HSCT Rate

HSCT rate is the proportion of responder per investigator's review (subjects who achieved either CMR or PMR during the treatment) who have undergone alloHSCT or autoHSCT while in remission and without any other anti-cancer treatment.

Objective Response (OR)

OR is determined **by the central review of radiographic assessment of PET-CT using Lugano Classification**. Subject's ORR status is determined by whether the subject achieves OR (CMR or PMR) during the first 12 weeks of treatment since starting blinatumomab.

Objective Response Rate (ORR)

Objective response rate (ORR) is the proportion of subjects who have achieved an OR (CMR or a PMR) **by the central review of radiographic assessment of PET-CT using Lugano Classification** among all subjects in the respective analysis set.

Overall Survival (OS)

It is calculated as the time from the first dose of blinatumomab until death due to any cause. Subjects who are alive at the date that triggers the analysis will be censored at the date last known to be alive.

Progression Free Survival (PFS)

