10.7.3 Exposure-Response Analysis

PK data of blinatumomab may be subjected to exploratory population PK analysis with data from multiple studies. Nonlinear mixed effects modeling will be used for the analysis. Effect of covariates on exposure will be determined. These may include, age, body weight, body surface area, renal function, liver function, and sex. Other covariates may be analyzed if necessary. Individual blinatumomab exposure at time of interest will be estimated with the population PK model and will be used for the exposure-response (E-R) analysis.

Exposure-response relationships for selected efficacy and safety endpoints may be assessed as appropriate. The objectives and methodology of the exposure-response analysis will be provided in an E-R SSAP.

11. Changes From Protocol-specified Analyses

Per Protocol: Response rates were defined based on radiographic assessment of PET-CT scans using the Lugano Classification. DOR, DOCR, PFS and HSCT related endpoints were based on radiographic assessment of PET-CT scans using the Lugano Classification.

Per SAP: Response rates will be based on **the central review of** radiographic assessment of PET-CT scans using the Lugano Classification. HSCT related endpoints will be based on **investigator's review of** radiographic assessment of PET-CT scans using the Lugano Classification. DOR, DOCR, and PFS related endpoints will be based on **investigator's review of** radiographic assessment of PET-CT scans using the **Lugano Classification and clinical assessment.**

12. Literature Citations / References

Brookmeyer R and Crowley J. A Confidence Interval for the Median Survival Time. *Biometrics*. 1982; 38: 29-41.

Clopper CJ and Pearson ES. The Use of Confidence or Fiducial Limits Illustrated in the Case of the Binomial. *Biometrika*. 1934; 26(4):404-413.

Gao, P, Ware, JH and Mehta, C Sample Size Re-estimation for Adaptive Sequential Design in Clinical Trials, *Journal of Biopharmaceutical Statistics*, 2008; 1184-1196.

Kalbfleisch JD and Prentice R L. *The Statistical Analysis of Failure Time Data*. New York: John Wiley & Sons; 1980.

13. Prioritization of Analyses

Not Applicable

14. Data Not Covered by This Plan

Not Applicable

15. Appendices

Appendix A. Technical Detail and Supplemental Information Regarding Statistical Procedures and Programs

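### The SAP defines DOR, duration of CMR and HSCT rates by investigator review but analyses them on a central-review responder set; the HSCT and mobilization rates each have two denominators

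*SAP*

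**What the plan says.** **Endpoint definitions.** SAP 4.1.2 lists "Duration of response (DOR) for subjects who achieved response per investigator's review during the first 12 weeks since starting blinatumomab" and "Duration of CMR for subjects who achieved CMR per investigator's review during the first 12 weeks since starting blinatumomab". The opening of SAP 6.2 says "DOR, DOCR, PFS and HSCT related endpoints will be based on investigator's review of radiographic assessment of PET-CT scans", and its DOR entry adds "Duration of Response is calculated only for subjects who achieve a response (CMR or PMR) per investigator's review". For transplant, 6.2 says "HSCT rate is the proportion of responder per investigator's review (subjects who achieved either CMR or PMR during the treatment". SAP section 11 records the choice as a change from the protocol: "HSCT related endpoints will be based on investigator's review of radiographic assessment of PET-CT scans using the Lugano Classification". It says the same of DOR, duration of complete response and PFS, with clinical assessment added.

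**Analysis set.** SAP 7.5 defines the Responder Analysis Set: "Includes all subjects who had CMR or PMR per central review during the first 12 weeks after initiation of blinatumomab".

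**Analysis text.** SAP 10.5.2 states "Duration of CMR and duration of response will be summarized with the KM summaries using Responder Analysis Set". It also bases the autologous, allogeneic and combined HSCT rates, and the mobilization rate, on the Responder Analysis Set. Sensitivity versions of the HSCT and mobilization rates use the Full Analysis Set (FAS).

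**Mobilization and NRM.** In 6.2 the mobilization denominator is the subjects who start mobilization in remission with no other anti-tumor therapy. For 100-day NRM, 6.2 admits only autologous transplants, while 10.5.2 takes subjects in either transplant set.

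**Protocol.** Section 10.1.1.2 starts phase 2 DOR from a centrally reviewed response in the first 12 weeks and leaves disease assessment in long-term follow-up to investigators.

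**The concern.** The endpoint and its analysis population are defined by different readers. Unless the two readers agree on every subject, the population in 10.5.2 is not the one for which the endpoint exists. Two programmers following the SAP could then report different subjects for DOR and duration of CMR, and different HSCT and mobilization rates. With 36 planned subjects the responder groups will be small, so a few discordant reads could visibly move a rate or a Kaplan-Meier curve. The trial is open-label, and an unresolved choice can be made after the results are known.

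**Working it through.** The plan states no figure to reproduce here, so the check sets the passages side by side and then shows the structure with symbols. All counts below are assumed; none comes from the documents.

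**1. Who is in which population.** Let b be responders by both reviews, i investigator-only and c central-only, within 12 weeks.

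- DOR is defined by 6.2 for b + i subjects.
- The 7.5 set holds b + c subjects.
- Only b subjects are in both.

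With b = 12, i = 2, c = 1: 14 subjects have a DOR, 13 are in the set and 12 are in both. SAP 10.5.2 uses the set for DOR and duration of CMR, for the HSCT rates and for mobilization. SAP 6.2 puts none of these on central review. ORR, which is centrally reviewed, falls to the FAS by the default in SAP 10.5. So the central-review set serves no central-review endpoint in 10.5.2.

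**2. HSCT rate.** Let T be the transplanted investigator responders and t those of them who are investigator-only.

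- Rate under 6.2: T/(b + i).
- Rate under 10.5.2, counted within the set: (T - t)/(b + c).

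Assume b = 12, T = 8, i and c each 0 to 3, and t from 0 to i:

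| i | c | t | 6.2 rate | 10.5.2 rate | Difference (points) |
|---|---|---|---|---|---|
| 0 | 0 | 0 | 8/12 = 66.7% | 8/12 = 66.7% | 0 |
| 2 | 1 | 0 | 8/14 = 57.1% | 8/13 = 61.5% | +4.4 |
| 2 | 1 | 1 | 8/14 = 57.1% | 7/13 = 53.8% | -3.3 |
| 2 | 1 | 2 | 8/14 = 57.1% | 6/13 = 46.2% | -11.0 |
| 3 | 0 | 0 | 8/15 = 53.3% | 8/12 = 66.7% | +13.3 |
| 3 | 3 | 3 | 8/15 = 53.3% | 5/15 = 33.3% | -20.0 |

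The last two rows are the extremes of the grid. If the numerator is not restricted to the set, the 10.5.2 rate is T/(b + c). The difference then runs from 8/15 - 8/12 = -13.3 (i = 0, c = 3) to 8/12 - 8/15 = +13.3 (i = 3, c = 0). SAP 10.5.2 also speaks of analysing the rates with the subjects in the transplant sets. Those sets hold only transplanted subjects, so taking them as denominators would give 100%.

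**3. Time window.** The 6.2 HSCT denominator covers response at any time on treatment; the 7.5 set stops at 12 weeks (day 84). Protocol 6.2.1 gives 56 infusion days and a scan 14 (+3) days later, so day 70 to 73. That leaves 84 - 73 = 11 to 84 - 70 = 14 days of slack. Protocol 6.2.2.2 and Table 6 footnote a do not count interruptions as infusion days. For other clinically relevant grade 3 events, Protocol 6.2.2.3 allows 14 days to improve plus 7 for logistical restart delay. A 14-day interruption puts the scan at day 84 to 87, and a 21-day one at day 91 to 94. A scan after week 12 is possible, not certain.

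**4. Mobilization.** Let M be the initiators, all within a set of R responders, with S successes. The 6.2 rate is S/M. The more natural reading of 10.5.2 gives S/R. Their ratio is (S/R)/(S/M) = M/R. For an assumed M/R of 1/2, 2/3 or 1, the 10.5.2 rate is 0.50, 0.67 or 1.00 times the 6.2 rate. If 10.5.2 means initiators within the set, the rates agree unless an initiator lies outside it.

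**5. NRM.** Autologous only against either transplant type is a direct contradiction and needs no arithmetic.

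**The case against.** The strongest objection is about direction. Sections 7.5 and 10.5.2 fit the protocol, which starts DOR from a central-review response, analyses it in the Responder Analysis Set (Protocol 10.5.3) and leaves later assessment to investigators. Central response with investigator-assessed progression is a coherent design, so the SAP could instead restore central review in 4.1.2 and 6.2. That stands as a possible repair for DOR. It does not remove the contradiction, and it runs against the choice the SAP records in section 11. That section describes the protocol rule only as radiographic assessment and so does not disclose the central-review start.

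Other limits also stand:

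- The HSCT range depends on assumed counts and on the numerator reading; the -20.0 extreme needs every investigator-only responder to be transplanted.
- Optional cycle 2 is open only to local responders, so a first investigator response cannot arise there, and the window matters only through a delayed cycle 1 scan. A 7-day interruption, the improvement limit for grade 3 cytokine release and neurologic events, gives day 77 to 80, inside week 12.
- Mobilization has a second reading under which the gap may vanish.
- The endpoints are descriptive, and DOR exists only for responders in any case.

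None of this reconciles the sections.

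**Conclusion.** The concern holds. As written, the SAP leaves out investigator responders who have a defined DOR, admits central responders who have none, and takes HSCT numerators from investigator-review sets (7.1, 7.2) that need not lie inside the central 12-week denominator. This is a contradiction, not missing detail. The assessor and NRM mismatches are certain from the text. The window and mobilization parts depend on a late scan and on how 10.5.2 is read.

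The effect on results cannot be sized, because the documents give no responder, discordance or mobilization counts; with full reader agreement the DOR conflict disappears. No test is attached to these endpoints. Central CMR on the FAS, the sample size, PFS and the FAS sensitivity analyses are unaffected. Those sensitivity analyses cover HSCT and mobilization only and do not settle which main rate is meant. The point should be fixed, but it does not threaten the trial's main conclusion.

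**What to change.** - Add to SAP section 7 a responder set defined by investigator review. Use it in 10.5.2 for DOR and duration of CMR (first 12 weeks; CMR subjects only for the latter) and for the HSCT rates, with one stated window and the numerator counted within the denominator.
- Keep the central-review set only for named central-review analyses; 10.5.2 has none at present.
- State one mobilization denominator in both 6.2 and 10.5.2, and report how many responders never started mobilization.
- Make the NRM population in 6.2 match 10.5.2.
- Record in section 11 that Protocol 10.1.1.2 starts DOR from a central-review response.
- Keep the FAS sensitivity analyses.

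The cost is SAP wording and one derived flag. No new data are needed, because Protocol 3.1 already has response assessed locally. The drawback is that responder status for these endpoints is then not independently reviewed in an open-label trial, which SAP section 11 has already accepted.
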